1 INTRODUCTION

CooperVision is evaluating the clinical performance of the MyDay toric contact lens in comparison with 1-Day Acuvue Moist for Astigmatism, and Dailies AquaComfort Plus Toric lenses, when each lens is worn on a daily disposable wear basis over one (1) week in a randomized bilateral, cross-over, dispensing study.

2 OBJECTIVES

The objective of the study is to evaluate the performance of MyDay toric test lens when worn on a daily disposable wear modality over 1 week.

The primary outcome variables are:

- Comfort and lens preference with respect to comfort (subjective ratings)
- Dryness and lens preference with respect to dryness (subjective ratings)
- Visual quality and lens preference with respect to visual quality (subjective ratings)

[REDACTED]

[REDACTED]

[REDACTED]

[REDACTED]

[REDACTED]

[REDACTED]

[REDACTED]

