4.8.3 DISPENSING LENS PAIR #1

The participant will be assigned a randomization ID and the first pair (lens pair #1) of contact lenses (either test or one of the control lenses) will be selected according to the randomization table.

- Lens pair #1 will be provided to participants in a manner which does not unmask the participant, as described in Section 4.7.4.
- The lenses will be inserted by the participant.
- The contact lenses will be allowed to settle for 10 minutes.
- The participant will be asked to give subjective binocular ratings for:
 - Comfort at insertion (0-10 scale)
 - Ease of insertion (0-10 scale)
 - Speed of settling (0-10 scale)
 - Visual quality (0-10 scale)
 - Vision stability (0-10 scale)
 - Overall satisfaction (0-10 scale)
- Monocular and binocular logMAR visual acuity will be recorded with high contrast letters under high (300-600 lux) and low (1-5 lux) room illumination.
- Lens surface and fit will then be assessed and graded according to the CVI grading scales for the following:
 - Lens wettability (0-4 scale)
 - Centration (mm)
 - Post-blink movement (mm)
 - Toric mark visibility

- Lens orientation (3 measurements per lens)
 - Overall stability of toric mark position
 - Overall lens fit acceptance (0-4 scale)
- The participant will be given a set of daily subjective questionnaires (Appendix 12) to be completed at home on days 1, 3 and 6 starting the morning after the dispensing visit (day 0), to reflect their lens wear experience at the time of rating. Participant will be given careful explanation of how and when to complete them. Questions will include:
 - Time of lens insertion and removal
 - Comfort after insertion (i.e. after lens settling), after 4, 8, and 12 hours, and just before lens removal (0-10 scale)
 - Dryness after 4, 8, and 12 hours, and just before lens removal (0-10 scale)
 - Visual quality/clarity after insertion (i.e. after lens settling), after 4, 8, and 12 hours, and just before lens removal (0-10 scale)
 - Vision stability after insertion (i.e. after lens settling), after 4, 8, and 12 hours, and just before lens removal (0-10 scale)

The participant will be asked to wear the study lenses for at least 12 hours per day and 6 days per week.

- Participant will be provided with sufficient contact lens supply.
- The participant will be discharged and reminded to return for the 1-week visit of lens pair #1 and to bring back all lens package foils.

4.8.4 1-WEEK FOLLOW-UP OF PAIR #1 & DISPENSING PAIR #2

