 - Overall dryness (0-10 scale)
 - Ease of insertion (0-10 scale)
 - Ease of removal (0-10 scale)
 - Overall visual quality/clarity (0-10 scale)
 - Overall visual stability (0-10 scale)

- Overall satisfaction (0-10 scale)
- Comments by participants
- Participants will be asked their preference between lens pair #1, lens pair #2, and lens pair #3, for a number of considerations:
 - Overall comfort preference
 - Visual quality preference
 - Vision stability preference
 - Overall handling (lens insertion and removal) preference
 - Overall lens preference
- Monocular and binocular logMAR visual acuity will be recorded with high contrast letters under high and low room illumination.
- Lens surface and fit will then be assessed and graded according to the CVI grading scales for the following:
 - Lens wettability (0-4 scale)
 - Centration (mm)
 - Post-blink movement (mm)
 - Toric mark visibility
 - Lens orientation (3 measurements per lens)
 - Overall stability of toric mark position
 - Overall lens fit acceptance (0-4 scale)
- The lenses will be removed and retained. The disposal procedures are detailed in Section 4.7.6.
- Slit lamp biomicroscopy will be assessed according to the CVI approved study biomicroscopy CRF.
- Exit visual acuity will be performed.
- The study exit form will be completed when a participant exits the study. This will occur either at study completion, or if the participant is discontinued from the study at another time. A study exit form must be completed for all participants who have taken a study ID

number. If in the opinion of the investigator post-study follow-up visits are required, the exit form will be completed after the last follow-up visit.

- The participant will be discharged and will sign the study completion forms and receive remuneration for participating in the study.

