4.9 SUMMARY OF STUDY PROCEDURES

Table 3 summarizes the visits and procedures for the study.

Table 3: Summary of visits and procedures for the study.

	Visit 1 Screening / Baseline & dispensing lens pair #1	Visit 2 (+3 days of scheduled visit) 1-wk follow-up of lens pair #1 / Dispensing lens pair #2	Visit 3 (+3 days of scheduled visit) 1-wk follow-up of lens pair #2 / Dispensing lens pair #3	Visit 4 (+3 days of scheduled visit) 1-wk follow-up of lens pair #3 / and Exit
Informed consent (screening)	√			
Confirmation of inclusion/exclusion criteria	√			
Ocular & medical history	√			
Demographics	√			
VA with spectacles or refraction	√	√	√	√
Auto-refraction & keratometry	√			
Sphero-cylindrical refraction	√			
Best corrected (sphero-cyl) VA monocular and binocular	√			
HVID, palpebral aperture size	√			
Biomicroscopy	√	√	√	√
Trial fitting of study lenses	√			
Wearing time on visit day		√	√	√
Symptoms & problems enquiry	√	√	√	√
Dispense new lenses	√	√	√	
Participant ratings completed	√	√	√	√
Take-home participant	√	√	√	

	Visit 1 Screening / Baseline & dispensing lens pair #1	Visit 2 (+3 days of scheduled visit) 1-wk follow-up of lens pair #1 / Dispensing lens pair #2	Visit 3 (+3 days of scheduled visit) 1-wk follow-up of lens pair #2 / Dispensing lens pair #3	Visit 4 (+3 days of scheduled visit) 1-wk follow-up of lens pair #3 / and Exit
ratings provided				
Surface assessments	√	√	√	√
Lens fit assessments	√	√	√	√
Over Refraction (dispense)	√	√	√	
VA with contact lenses	√	√	√	√
Assessment of adverse events	√	√	√	√
Complete take home questionnaires	On days 1, 3, and 6.			
Return questionnaires		√	√	√
Exit Study				√

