9 DEVICE MALFUNCTIONS

A device malfunction means the failure of the device to meet its performance specification or otherwise perform as intended. *Any defective lens that is likely to cause or contribute to a Serious Adverse Event should be reported to the Principal Investigator and the sponsor **within 24 hours** of the investigator becoming aware of the malfunction. The ORE would also be notified within 24 hours of any device malfunction that may contribute to a Serious Adverse Event.*

Other defective lenses should be reported to the Sponsor as soon as possible (usually in weekly study updates to the Sponsor).

This clinical study will also ascertain satisfaction or preference with subjective attributes such as comfort, vision, or lens handling. Responses to these subjective questionnaires will not be considered as complaints or device malfunctions.

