11.2 STATISTICAL ANALYSIS

All data will be analyzed by the CCLR at the University of Waterloo. Summary statistics will be produced (e.g. mean, standard deviation). Data analysis will be conducted using Statistica and / or SPSS. Descriptive statistics will be provided on information regarding baseline variables (age, gender, refractive error distribution, etc.). Analysis of variables will be conducted separately on each eye, and data will not be pooled. A Binomial test will be used to analyze the results for the count data of subjective preferences. The number of “no preference” will be evenly distributed to the two options on the basis they would be equally likely to choose either.

Table 5 lists the primary outcome variables and anticipated statistical procedures.

Table 5: Outcome variables and anticipated statistical procedures

Variable	Analysis	Statistical test
Analogue scales/Numeric scales/Preference scales/VA Lens parameters, Biomicroscopy (continuous variables)	Effect of lens type	RMANOVA/MANOVA/ Friedman /Wilcoxon matched pairs test Tukey HSD post hocs Paired t-test Chi-square test
Biomicroscopy (ordinal variables)	Effect of lens type	Friedman Wilcoxon matched pairs test
Analogue scales/Numeric scales/Lens parameters, Biomicroscopy (continuous)	Relationship between slit lamp findings and analogue scales	Pearson correlation - r
Biomicroscopy (ordinal variables)	Relationship between slit lamp findings and analogue scales	Spearman correlation - rho

The critical alpha level for statistical significance will be set at $p \leq 0.05$, with no adjustments for multiple comparisons.

All participants who were evaluated will be used in the analysis. In the event of missing data, individual data points will be excluded in the analysis and not extrapolated from the collected data.

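### Lens preference for dryness is a primary outcome, but the listed study procedures never ask for it

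*Combined protocol and SAP*

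**What the plan says.** Section 2 (Objectives) sets out the primary outcome variables as three parallel pairs, each a rating and a preference. The pair for dryness reads "Dryness and lens preference with respect to dryness (subjective ratings"). The pairs for comfort and for visual quality take the same form.

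The preference questions appear in Section 4.8.6, at Visit 4, once all three lens pairs have been worn: "Participants will be asked their preference between lens pair #1, lens pair #2, and lens pair #3, for a number of considerations". Five items follow: overall comfort, visual quality, vision stability, overall handling, and overall lens preference.

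Dryness is collected elsewhere as a score. The take-home questionnaire in Section 4.8.3 asks for "Dryness after 4, 8, and 12 hours, and just before lens removal (0-10 scale"), on days 1, 3 and 6 of each wearing period. An overall dryness score on the same scale is taken at Visits 2, 3 and 4 (Sections 4.8.4 to 4.8.6).

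On analysis, Section 11.2 states: "A Binomial test will be used to analyze the results for the count data of subjective preferences". It also says how responses expressing no preference are to be shared out. Table 5 in that section names preference scales among the variables for several general tests.

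**The concern.** The objectives and the procedures do not match. A primary outcome needs a defined source of data, and under the listed procedures dryness preference has none. The planned test would therefore have nothing to work on.

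The gap is hard to repair afterwards. A choice among three lenses can be made only when all three have been worn, and the visit at which that becomes possible is also study exit. If the question is not asked then, two courses remain, and both are poor unless declared in advance:

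- **Infer a preference from the dryness scores.** This is a different measure from a stated choice. The rule (which scores, which days, how ties are treated) would be picked after the data exist.
- **Leave the outcome out of the report.** Without a documented amendment, that is an undeclared change to a primary outcome.

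**Working it through.** This is a check of consistency, so the main step is to set the sections side by side.

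**1. Match each primary outcome to its source.**

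| Primary attribute (Section 2) | 0-10 rating collected? | Preference item at Visit 4 (Section 4.8.6)? |
|---|---|---|
| Comfort | Yes | Yes |
| Dryness | Yes | **No** |
| Visual quality | Yes | Yes |

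The primary preferences are {comfort, dryness, visual quality}. The Visit 4 items are {comfort, visual quality, vision stability, handling, overall}. The first set less the second leaves {dryness}. So 2 of 3 primary preferences are covered. Counting ratings and preferences separately (3 + 3 = 6), 1 of 6 primary variables has no source.

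**2. Count the planned dryness data per participant.**

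- Take-home ratings: 3 lens pairs × 3 days × 4 time points = 36 at most.
- Overall ratings at Visits 2, 3 and 4: 3.
- Total ratings: 36 + 3 = 39 at most.
- Dryness preference responses in the listed procedures: 0.

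The Binomial test on dryness preference would thus have n = 0. The comfort and visual quality preferences have a target of 45 completers and a maximum of 52 participants (Section 4.6.1).

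**3. Look for another explanation in the text.**

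- *Redaction.* The blacked-out lines in Section 2 come after the three visible outcomes. The Visit 4 list shows no redaction.
- *A list of examples only.* The ratings list at the same visit points to a form (Appendix 11) and is worded as what that form includes. The preference list cites no form and is not worded as examples.
- *Preference meant as something derived from ratings.* Section 2 attaches the same parenthesis about subjective ratings to all three outcomes, yet comfort and visual quality each have a direct preference question. Section 11.2 gives no derivation rule, and its handling of undecided responses fits stated choices.
- *Asked elsewhere.* Table 3 has a row for "Participant ratings completed" but no preference row for any attribute. Section 9 says "This clinical study will also ascertain satisfaction or preference with subjective attributes such as comfort, vision, or lens handling", an open list that does not name dryness. Neither supplies the item.
- *Free-text comments.* Section 12.6 excludes recorded comments from data analysis.

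**4. Sample size, for completeness.** Table 4 rests on comfort scores. A two-sided paired t-test with 80% power, a difference of 5 and an SD of 12.6 gives 52 participants at alpha 0.05 and 41 at alpha 0.10, as the plan states. Nothing in this point changes those figures.

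**The case against.** The strongest reply is that what matters in practice is the form completed at Visit 4, and the forms are not in the text reviewed. This protocol leans heavily on appended forms. If the exit preference form has a dryness question, the data will be collected and only the protocol text is incomplete. This limit stands: the zero count describes the procedures as listed and does not predict what the form will gather. It does not remove the contradiction, because Section 4.8.6 neither lists the item nor points to a form that does.

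The silence of Table 3 and Section 9 is also weak evidence. Table 3 omits preference for every attribute, including those that are asked about, and Section 9 gives examples only, in a passage about complaints. That is fair. The point rests on Sections 2 and 4.8.6; the other two show only that the item is not supplied elsewhere.

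Table 5 puts preference scales under several other tests as well as the Binomial test planned in the text, so the meaning of preference is not fully settled. That is true, but Table 5 adds neither a dryness question nor a way to derive one.

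Finally, dryness is still compared across lenses through within-person ratings, so the loss is partial. That is correct and limits the size of the problem. It does not supply the preference that Section 2 names as primary.

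**Conclusion.** The concern holds. As written, the plan names three primary preference outcomes and provides questions for two. Dryness preference has no source question, no derivation rule and, under the listed procedures, no observations for its planned test. This is a contradiction to be resolved before participants reach Visit 4, because the response cannot be collected in the planned way after exit.

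The effect is confined to 1 of 6 primary variables. The dryness ratings, the comfort and visual quality outcomes, and the sample size are untouched. The conclusion assumes that the list in Section 4.8.6 is what will be asked. A dryness item on the exit form would reduce the matter to a correction of the text.

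**What to change.** 1. Compare the exit preference form with the primary outcomes in Section 2.
2. Add an overall dryness preference item to the list in Section 4.8.6, and to the form if it is absent there, before participants reach Visit 4.
3. If that can no longer be done, remove dryness preference from the primary outcomes by a dated, documented amendment made before any unmasked look at results, and report it as not collected. Do not substitute a preference inferred from the ratings under a rule chosen later.

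The cost is one line of protocol text and, if the form lacks the item, one more question at a visit already scheduled. No extra visit is needed and the sample size does not change.

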3 HYPOTHESIS

The study hypothesis is that the MyDay toric test lens (MD-T) will perform as well or better clinically than the two control lenses: 1-Day Acuvue Moist for Astigmatism (1-DAM-T) and Dailies AquaComfort Plus Toric (DACP-T).

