4.6 STUDY POPULATION

4.6.1 NUMBER OF PARTICIPANTS

Up to 52 participants will be dispensed / randomized with study products, with a target of 45 completing the study. Participants will be recruited using CCLR records and advertising approved by the UW Office of Research Ethics (Appendices 2, 3a, and 3b). Each participant will be given a unique ID number. Additionally, all participants must meet the study inclusion and none of the exclusion criteria listed below.

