Participants will be asked to wear lenses for at least 4 hours prior to the visit appointment. Participants who attend without lenses in-situ (wearing lenses) for at least four hours will be rescheduled.

- The participant will be asked to score their subjective responses by reflecting on a typical day during the previous week of lens wear, as detailed in the subjective ratings form (Appendix 11) and includes the following:
 - Wear time at this visit (hours)
 - Wear time per day during previous 1 week (hours)
 - Comfortable wear time per day during previous 1 week (hours)
 - Overall comfort (0-10 scale)

- Overall dryness (0-10 scale)
 - Ease of insertion (0-10 scale)
 - Ease of removal (0-10 scale)
 - Overall visual quality/clarity (0-10 scale)
 - Overall visual stability (0-10 scale)
 - Overall satisfaction (0-10 scale)
 - Comments by participants
- Monocular and binocular logMAR visual acuity will be recorded with high contrast letters under high and low room illumination.
 - Lens surface and fit will then be assessed and graded according to the CVI grading scales for the following:
 - Lens wettability (0-4 scale)
 - Centration (mm)
 - Post-blink movement (mm)
 - Toric mark visibility
 - Lens orientation (3 measurements per lens)
 - Overall stability of toric mark position
 - Overall lens fit acceptance (0-4 scale)
 - The lenses will be removed and retained. The disposal procedures are detailed in Section 4.7.6.
 - Slit lamp biomicroscopy will be assessed according to the CVI approved study biomicroscopy CRF.
 - There will be a 10 minute wash-out before insertion of lens pair #2.
 - Lens pair #2 will be provided to participants in a manner which does not unmask the participant, as described in Section 4.7.4.
 - The lenses will be inserted by the participant.
 - Procedures of fit and assessment will be repeated as detailed in the dispensing visit, section 4.8.3.
 - The participant will be discharged and reminded to return for the 1-week visit of lens pair #2 and to bring back all lens package foils.

4.8.5 1-WEEK FOLLOW-UP OF PAIR #2 & DISPENSING PAIR #3

Participants will be asked to wear lenses for at least 4 hours prior to the visit appointment. Participants who attend without lenses in-situ (wearing lenses) for at least four hours will be rescheduled.

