11 STATISTICAL ANALYSIS AND DATA MANAGEMENT

11.1 SAMPLE SIZE CALCULATION

The maximum sample size will be 52. For a two-sided paired t-test with an alpha of 0.05 and a power goal of 80%, this will allow an effect size as small as 0.28 to be detected. This sample size will give approximately 80% confidence to detect a difference of 5 points in comfort ratings.

Table 4 shows the sample size determination for a difference between two means in comfort scores. Sample sizes with 80% power are shown at two different alpha levels (alpha = 0.05 and alpha = 0.10). Assuming a standard deviation of 12.6 points, a sample size of 52 participants provides 80% power to detect a trend in difference of comfort scores between 5 points on a 100-point scale.

Table 4: Sample size calculation

Mean individual	Mean individual	Sample size	Sample size
-----------------	-----------------	-------------	-------------

difference in score	standard deviation	(p = 0.05)	(p = 0.10)
5	12.6	52	41
7	17.6	52	41

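### The hypothesis is that MD-T does as well as or better than both controls, but the plan tests only for differences, with no margin or confidence-interval rule, so the "as well" half has no valid test.

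*Combined protocol and SAP*

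**What the plan says.** - **Hypothesis (section 3).** MD-T "will perform as well or better clinically than the two control lenses". This is the only hypothesis stated, and it names both controls.
- **Sample size (section 11.1).** The basis is given as follows: "For a two-sided paired t-test with an alpha of 0.05 and a power goal of 80" per cent. The target is a 5-point difference in comfort on a 100-point scale. The text reads "Assuming a standard deviation of 12.6 points" and gives 52 participants. It also says of 52 that "this will allow an effect size as small as 0.28 to be detected". Table 4 gives 52 (alpha 0.05) and 41 (alpha 0.10) for two rows: 5 points with SD 12.6, and 7 points with SD 17.6.
- **Analysis (section 11.2, Table 5).** The effect of lens type is tested by repeated-measures ANOVA or MANOVA, Friedman, Wilcoxon, paired t or chi-square tests, and preferences by a binomial test. Table 5 includes "Tukey HSD post hocs". Significance is judged at 0.05, "with no adjustments for multiple comparisons".
- **Numbers (section 4.6.1).** Up to 52 are randomised, "with a target of 45 completing the study".
- **Scale (sections 4.8.4 to 4.8.6).** Overall comfort is collected at each 1-week follow-up on a 0-10 scale, not on the 100-point scale used for the sample size.

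**The concern.** Performing as well as a control is a claim that any deficit is too small to matter. It needs a stated limit and evidence that excludes anything worse. Every lens comparison in section 11.2 has no difference as its null hypothesis, so a significant result can show that MD-T is better or worse, and a non-significant one shows neither equality nor non-inferiority. Section 11.1 calls the 5 points a difference to detect, so they cannot be taken as a margin.

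If non-significance became the default evidence, a smaller or noisier trial would confirm the hypothesis more easily. A margin chosen after the results are known would not be credible, so the gap has to be closed beforehand. Data collection is not affected. What is at stake is whether the trial can validly conclude half of its only hypothesis.

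**Working it through.** **Inputs.** Difference 5 points, SD of paired differences 12.6, two-sided alpha 0.05, n = 52 (section 11.1); n = 45 completers (section 4.6.1). The correlation between the two MD-T-minus-control differences is not in the documents. I assume 0.5 and show 0.3 to 0.7. Paired differences are taken as normal. Pairs of results are in the order 45 / 52 completers.

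**1. The plan's sample size.** Standardised difference = 5/12.6 = 0.397; for the second row of Table 4, 7/17.6 = 0.398. Exact paired-t power (noncentral t, n − 1 df, noncentrality = standardised difference × √n) first reaches 80% at n = 52 for alpha 0.05 and n = 41 for alpha 0.10, in both rows. Table 4 reproduces, as the sample size of a difference test.

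**2. The stated effect size.** At n = 52 the standardised difference detectable with 80% power is 0.396. Power for 0.28 is 51%, and 80% power for 0.28 would need 103 participants. So 0.28 does not match the rest of section 11.1. It equals 0.397/√2 = 0.281, which suggests a conversion slip.

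**3. If non-significance were read as "as well".** Take a true deficit of 5 points.
- Noncentrality: 0.397 × √45 = 2.66 and 0.397 × √52 = 2.86. Critical t: 2.015 and 2.008.
- Against one control, P(not significant) = 0.260 / 0.198.
- Two controls, by simulation of correlated paired differences with estimated SDs:

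| True state | Neither test significant, 45 completers | 52 completers |
|---|---|---|
| 5 points worse than one control, equal to the other | about 24% | about 18% |
| 5 points worse than both | 13% (10-16%) | 9% (6-11%) |

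Brackets give the range for correlation 0.3 to 0.7. The first row hardly moves over that range.

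**4. A confidence-interval rule with a candidate 5-point margin.** The half-width of the 95% interval is 2.015 × 12.6/√45 = 3.8 and 2.008 × 12.6/√52 = 3.5 points.
- False conclusion: when the true deficit against a control equals the margin, that control's interval excludes a larger deficit 2.5% of the time. Requiring both controls to pass cannot raise this.
- Power at true difference 0, one control: 74% / 80%.
- Power at true difference 0, both controls: about 61% (58-64%) / 69% (67-71%).

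**5. If Tukey HSD decides the contrasts.** Critical value q(3)/√2 = 2.38 on 2(n − 1) df, sphericity assumed. Power for a 5-point difference is 61% / 69%, against 74% / 80% for the unadjusted paired t-test on which the trial is sized.

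**The case against.** **The harm is conditional.** Section 2 says only that performance will be evaluated, Table 5 calls its procedures anticipated, and section 6 describes a minimal-risk study of marketed products. A reader might infer that the plan intends to treat non-significance as proof of "as well". The text does not say so, and the miss rates apply only if it is read that way. This stands, and it makes rewording section 3 as valid a repair as adding a margin. It does not remove the gap, because section 3 as written makes a claim that section 11.2 cannot test.

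**Redaction.** Lines are blacked out after the primary outcomes in section 2. Sections 3, 11.1 and 11.2, where a margin or decision rule would be expected, show none.

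**A larger SD.** A reader might work back from 0.28 to an SD of 5/0.28 = 17.9 and conclude that a 5-point deficit would be missed about half the time. The documents do not support this. Section 11.1 gives 12.6 in the text and in Table 4, and 12.6 reproduces both 52 and 41. The 17.6 in Table 4 belongs to a 7-point difference.

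**Tukey against no adjustment.** This might be taken as a flat contradiction. The sentence on adjustment can also mean none across the many outcomes, with Tukey used among lenses within one outcome. It is an ambiguity to clear up.

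**Limits of a margin rule.** The primary outcomes pair ratings with preferences, comfort is also rated at dispensing and at home on days 1, 3 and 6, and no visible text names the primary time point. Table 5 also allows rank tests. A rule on one rating therefore has to say what role the rest play and how the interval is calculated.

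**Conclusion.** The point holds. The plan can support "better" but has no valid test for "as well", because it gives no margin and no interval rule. Were non-significance used instead, a true 5-point deficit against one control would pass 26% / 20% of the time at 45 / 52 completers. A deficit against one control with equality to the other would pass about 24% / 18% of the time. An interval rule at that margin holds the error to 2.5% or less.

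These figures rest on SD 12.6, normal paired differences on the 100-point scale and, for two controls, an assumed correlation of 0.5. The 5-point margin is only a candidate that the documents do not endorse. The 0.28 in section 11.1 is a separate error and does not invalidate the 52. The results do not show that enrolment must rise.

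**What to change.** 1. **Before unmasking, choose one of two routes.**
   - (a) In section 11.2, conclude "as well" on the 1-week overall comfort rating only if the two-sided 95% confidence interval for MD-T minus each control excludes a deficit larger than a pre-stated, justified margin, for both controls. Claim "better" than a given control when that control's interval also excludes zero in MD-T's favour. State the margin on the 0-10 scale collected (5 of 100 is 0.5 if rescaled linearly) and the interval method if rank tests are used. Say whether the other primary ratings and the preferences are confirmatory or supportive.
   - (b) Reword section 3 as a difference or estimation hypothesis, report confidence intervals, and state that non-significance will not be read as "as well".
2. **Section 11.1.** Replace 0.28 with about 0.40. Under (a), restate the power of the new rule at SD 12.6 for 45 and 52 completers, using the chosen margin, rather than raise enrolment.
3. **Secondary.** State whether Tukey HSD or the unadjusted paired contrast decides the MD-T comparisons. If Tukey decides, restate the power.

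**Cost.** Wording in section 3 or sections 11.1 and 11.2, with no new visits or data. Route (a) means publishing a power below the 80% goal for both controls together. Route (b) gives up a formal claim of "as well".
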